7 STATISTICAL METHODS

7.1 Study Reporting

There will be two reporting events for this study, one reporting when all subjects complete Month 6 visit and another reporting when all subjects complete the study (Month 12 visit). For the first reporting, when all subjects complete the Month 6 visit, data will be cleaned and frozen at the subject visit level. The sponsor will be unmasked for the 6 months efficacy and safety analyses. AE starting after the Month 6 visit will not be included for Month 6 reporting for better risk-benefit assessment. All other data after Month 6 visit will be included and reported as they are. For the second data reporting, when all subjects complete the entire 12-month study, data will be cleaned, and the database will be locked.

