8.3 Rescue Therapy

Subjects whose clinical status declines in the study eye may be evaluated for rescue surgery by Standard of Care Keratoplasty [Descemet membrane endothelial keratoplasty (DMEK), Descemet stripping endothelial keratoplasty (DSEK), or penetrating keratoplasty (PK)].

Consultation with the Medical Monitor is required prior to any procedure. Evaluation will include the subject's visual symptoms, problems, or complaints, and ocular examination findings as available. Subjects who undergo a rescue procedure should be followed for approximately 1 month and may be discontinued from the study thereafter.

All decisions involving rescue surgery should be documented in the eCRF. In addition, all post-rescue follow-up visits should be documented in the eCRF.

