6.5 Unscheduled visits

All by-visit assessments will be summarized and presented using the nominal visit provided in the data. Programmatic visit windows will not be used, unless otherwise specified.

Unscheduled visits will be used in the determination of baseline. All data, including unscheduled visits, will be present in data listings.

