7.9 Handling of Data after Rescue

For this study reporting, any data collected at and after rescue visits will not be used for the analyses and summary tables but will be included in the listings. This applies to both efficacy and safety tables as well as concomitant medication tables. The only exception is that adverse events collected at and after rescue visits will be summarized separately as described in Section 14.1.

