14 SAFETY ANALYSES

14.1 Adverse Events

Adverse events will be coded using Medical Dictionary for Regulatory Activities (MedDRA) version 26.1.

Treatment-emergent adverse events (TEAEs) are defined as any adverse events that occur during or after the Day 1 injections, or any adverse events that are continuous from the screening but worsen during or after the Day 1 injections.

Ocular and non-ocular TEAEs will be summarized separately. Summary of ocular TEAEs will be separated by study eye and non-study eye.

An overall summary including the number of events and the number and percentage of subjects who experienced at least one TEAE will be presented by treatment group and overall. The overall summary will also include at least one serious TEAE, treatment-related TEAE, treatment-related serious TEAE, TEAE leading to subject discontinuation from the study, and TEAE leading to death.

TEAEs will be summarized by System Organ Class (SOC) and Preferred Term (PT). Subjects are counted only once under each SOC or PT for which they have at least one TEAE.

Summaries by relationship to study product, by relationship to study procedure and by maximum severity will also be provided.

Serious TEAEs will not be summarized in table format as it is anticipated number of serious TEAEs will be very limited.

In addition, the following AE summaries will be provided for AEs collected at and after rescue visits:

- Overall summary of TEAE
- TEAE by SOC and PT

For these summaries, denominators to be used for percentage calculation will be number of Rescued subjects.

All AEs will be presented in a subject listing with a flag indicating TEAE and a flag indicating AEs occurred at and after rescue visits. In addition, all serious AEs will be presented in a separate listing.

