14.3 Rescue Surgery

Rescue surgeries include rescue surgeries given by the investigators even when the rescue criteria were not met.

The number of rescue surgeries will be summarized descriptively by visit. Use of rescue surgeries will be presented in a listing.

Time to rescue surgery is defined as the time duration from Day 1 to rescue date plus 1 for rescue subjects, and from Day 1 to last visit plus 1 for non-rescue subjects.

Medians with 95% CI of time to rescue surgery will be provided and Kaplan-Meier plots will be produced. Time to rescue surgery will be presented in a listing.

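### In the Month 6 report, the post-rescue AE percentage has a numerator cut at the Month 6 visit and a denominator with no cut, so late rescues pull it down

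*SAP*

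**What the plan says.** SAP 7.1 plans two reports, the first when every subject has completed Month 6 and the second when every subject has completed Month 12. For the first it sets two different cut-offs in consecutive sentences. On adverse events: "AE starting after the Month 6 visit will not be included for Month 6 reporting for better risk-benefit assessment". On everything else: "All other data after Month 6 visit will be included and reported as they are".

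SAP 7.9 removes data collected at and after rescue visits from the tables; such data "will not be used for the analyses and summary tables but will be included in the listings". Post-rescue AEs are the one exception. They get their own summaries in SAP 14.1 (an overall summary, and a table by system organ class and preferred term), with this rule: "For these summaries, denominators to be used for percentage calculation will be number of Rescued subjects".

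Rescue surgery is reported separately from AEs, in SAP 14.3. Protocol 8.3 sets no time limit on rescue, and it plans the follow-up: "Subjects who undergo a rescue procedure should be followed for approximately 1 month and may be discontinued from the study thereafter".

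**The concern.** Rescue surgery is not an AE record, so under SAP 7.1 it belongs to the other data that are kept after Month 6. The SAP 14.1 denominator has no date limit, so it takes in every rescue known at the data cut. The numerator takes in only AEs that start by the Month 6 visit. For a subject rescued after Month 6, the whole planned month of post-rescue follow-up lies beyond the AE cut. That subject adds one to the denominator and can add almost nothing to the numerator.

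The result is a post-rescue AE percentage that looks better than the data behind it, in the report that SAP 7.5 calls the primary efficacy analysis. The shortfall need not be equal across arms. Protocol 4.5 reports that, in the El Salvador experience, cells alone did worse than cells with Y-27632 on several measures, need for rescue among them. Late rescues could therefore differ by arm here too, and part of an arm difference in this table could come from the cut-offs alone.

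**Working it through.** The plan states no figure for this percentage, so there is none to reproduce. The check has two parts: the algebra, which needs no assumptions about rates, and an illustration of size, in which every rate is assumed.

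**Algebra**

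- R = subjects rescued on or before their Month 6 visit.
- L = subjects rescued after it but before the data cut for the first report.
- E = those in R with a post-rescue TEAE starting by Month 6.
- As written (SAP 7.1 with 14.1): E/(R+L).
- One cut-off for both parts: E/R.
- Ratio of the two: R/(R+L), which is below 1 whenever L > 0.

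Example with R = 4, E = 2 (assumed counts): aligned 2/4 = 50.0%. As written, L = 1 gives 2/5 = 40.0%, L = 2 gives 2/6 = 33.3%, and L = 4 gives 2/8 = 25.0%.

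Two arms with the same aligned rate of 50%: R = 6, L = 0, E = 3 shows 3/6 = 50.0%; R = 2, L = 4, E = 1 shows 1/6 = 16.7%. The gap comes only from the cut-offs.

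One qualification: SAP 14.1 selects AEs by when they are collected, and SAP 7.1 cuts them by when they start. An AE that began before Month 6 but was first collected at a later rescue visit could still enter the numerator. Late-rescued subjects therefore contribute almost nothing, not strictly nothing.

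**Illustration of size**

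Assumptions, none of them from the documents: share rescued by Month 6, p6 = 0.20; true post-rescue AE rate 40%; uniform accrual over A months. Time on study at the cut is 6 + min(6, U) months, with U uniform on (0, A), because the first report waits for the last subject's Month 6 visit and follow-up ends at Month 12.

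- Constant rescue hazard: λ = −ln(1 − p6)/6 = −ln(0.80)/6 = 0.0372 per month.
- S̄ = mean of exp(−λ(6 + min(6, U))).
- Late rescues = (1 − p6) − S̄; all rescues = 1 − S̄; late share f = late/all.
- Percentage shown = 0.40 × (1 − f).

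For A = 12: S̄ = 0.6785, late = 0.80 − 0.6785 = 0.1215, all = 0.3215, f = 0.378, shown = 0.40 × 0.622 = 24.9%. In 100 subjects that is about 12 late rescues out of 32.

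| Accrual (months) | f, constant hazard | Shown | f, rescues mostly early (Weibull shape 0.5) | Shown |
|---|---|---|---|---|
| 1 | 0.068 | 37% | 0.035 | 39% |
| 3 | 0.177 | 33% | 0.093 | 36% |
| 6 | 0.293 | 28% | 0.159 | 34% |
| 12 | 0.378 | 25% | 0.21 | 31–32% |
| 18 | 0.402 | 24% | 0.230 | 31% |

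Changing p6 to 0.10 or 0.30 under constant hazard with 12-month accrual gives 24% or 26%, so the result depends little on p6.

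A simulation that also models the one-month follow-up of Protocol 8.3 (constant hazard, p6 = 0.20, 12-month accrual, 40% AE risk over a full month) gives about 39% with all AEs to the data cut, 23% as written, and 37% with both parts cut at Month 6. The common cut-off removes nearly all of the shortfall.

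**The case against.** The strongest reply is that a reader of the same report can rebuild the aligned figure. SAP 14.1 gives counts as well as percentages and flags AEs at and after rescue in the listing; SAP 14.3 lists time to rescue for each subject; SAP 6.4 puts study day in the listings. That is true, and it lowers the severity, but the printed percentage stays wrong for anyone who reads only the table. A second reply is that freezing data at the subject-visit level implies a Month 6 cut for everything. It does not, because "All other data after Month 6 visit will be included and reported as they are" admits later data expressly. A third is that every rate in the illustration is assumed. That also stands: with 20 subjects per arm and constant hazard, late rescues per arm would be about 20 × 0.0147 = 0.3 with 1-month accrual and 20 × 0.1215 = 2.4 with 12-month accrual.

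A reader might infer more than the documents support:

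- **That the AE cut is itself a fault.** It fits Protocol 10.1, which describes 6-month analyses. The AEs are deferred to the Month 12 report, and SAE reporting under Protocol 9.5 is untouched.
- **That the SAP 14.3 rescue analyses are distorted.** The counts are by visit and can be read up to Month 6. Following non-rescued subjects "from Day 1 to last visit plus 1 for non-rescue subjects" is ordinary censoring, and later follow-up does not change a Kaplan-Meier curve before Month 6.
- **That late AEs vanish from the listings.** SAP 7.1 does not limit its cut to tables, but SAP 14.1 lists all AEs and adds "In addition, all serious AEs will be presented in a separate listing", and SAP 6.5 says "All data, including unscheduled visits, will be present in data listings", although under a heading on unscheduled visits. A clarifying phrase would help; no suppression is shown.
- **That SAP 15 conceals a protocol change.** Protocol 10.1 does not bar later data from the first report, so including them is added detail.

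**Conclusion.** Wrong as written, and minor. Followed literally, SAP 7.1 and 14.1 give E/(R+L) where E/R is meant, and no section aligns the two. The percentage is too low whenever L > 0 and E > 0, and by different amounts in different arms if late rescues differ. That conclusion rests on the text alone.

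The size does not. For a true rate of 40% and 20% rescued by Month 6, both assumed, the table would show from about 39% (early-weighted rescues, 1-month accrual) down to 24% (constant hazard, 18-month accrual). If nobody is rescued between Month 6 and the data cut, the error is zero. The primary comparison is unaffected, the analyses are descriptive (SAP 7.3 and 7.4), and only the first report is touched.

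**What to change.** Add one sentence to SAP 14.1: for the Month 6 report, the post-rescue AE summaries count in the denominator only subjects rescued on or before their Month 6 visit, and in the numerator only AEs with onset up to that visit. SAP 14.3, the time-to-rescue analysis and SAP 15 need no change.

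The data are already collected, so the cost is the sentence and one filter in the table program. The downside is that post-rescue AEs of late-rescued subjects wait for the Month 12 tables, as SAP 7.1 already implies.

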7.2 Unit of Analysis

The unit of analysis in this study will be the study eye for all efficacy and ocular safety summaries. Additionally, non-ocular adverse events (AEs) and medical history will be presented at the subject level.

The non-study eye safety summaries will also be presented as appropriate.

7.3 Sample Size Determination

This study is not powered to show statistical significance but will provide initial estimates and trends of the endpoints for use in future trial designs. The sample size will allow for safety information to be obtained, while still limiting the number of subjects exposed to the IP. Statistical analysis will be descriptive.

7.4 Statistical Significance

All statistical testing will be done at the two-sided alpha level of 0.05. As this is a Phase 1/2 study, no adjustments to alpha will be made for the tests of multiple comparisons and multiple endpoints. Statistical analysis will be descriptive.

7.5 Interim Analysis

As stated in Section 7.1, there will be an interim reporting when all subjects complete the primary endpoint at Month 6. As this analysis is for all subjects completing the primary endpoint, this analysis is considered the study primary efficacy analyses. And hence, there will not be alpha adjustment. All p-values will be judged at 2-sided alpha level of 0.05. All p-values are considered nominal.

7.6 Statistical Hypothesis

This is a Phase 1/2 study. No formal statistical hypothesis is considered.

7.7 Adjustments for Multiplicity

7.8 Adjustment for Covariates

Change from baseline in BCVA and CCT at Month 6 will be analyzed using Analysis of covariance (ANCOVA) for the full analysis set. Baseline of BCVA and CCT will be used as covariate for the adjustment.

7.9 Handling of Data after Rescue

For this study reporting, any data collected at and after rescue visits will not be used for the analyses and summary tables but will be included in the listings. This applies to both efficacy and safety tables as well as concomitant medication tables. The only exception is that adverse events collected at and after rescue visits will be summarized separately as described in Section 14.1.

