10.8 Safety Analyses

All safety analyses will be conducted on the Safety Analysis Set. No formal statistical tests of treatment difference are planned.

AEs will be coded using the Medical Dictionary for Regulatory Activities TEAEs (i.e., AEs that begin or worsen in severity after initiation of study drug) will be summarized by treatment arm and overall, in the study eye. Non-ocular TEAEs will also be summarized. Additionally, TEAEs and serious AEs will be summarized in a similar manner by maximum severity and relationship to study drug and the surgical procedure.

Changes from baseline of quantitative measurements (ophthalmic evaluations, laboratory findings) will be summarized by treatment arm and timepoint.

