4.2.2 Safety Evaluations

- Incidence and severity of ocular treatment-emergent adverse events (TEAEs)
- Incidence and severity of non-ocular TEAEs
- Loss from baseline in BCVA ≥ 15 letters
- Rescue rate and time to rescue

- Graft rejection

The safety evaluations will be based on adverse event (AE) reporting, laboratory findings (clinical chemistry and hematology), and ophthalmic examinations, including Goldmann tonometry, Slit Lamp biomicroscopy, gonioscopy, dilated fundoscopy, and BCVA (as measured by ETDRS).

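### Adverse events after rescue are tabulated only over rescued subjects, so no planned table gives all TEAEs, or their maximum severity and relationship, per treated subject by arm

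*SAP*

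**What the plan says.** SAP 7.9 sets one rule for every output: "any data collected at and after rescue visits will not be used for the analyses and summary tables but will be included in the listings". It names efficacy, safety and concomitant-medication tables as covered. One carve-out follows: "The only exception is that adverse events collected at and after rescue visits will be summarized separately as described in Section 14.1".

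SAP 14.1 describes the main TEAE tables: an overall summary, a table by system organ class and preferred term (SOC/PT), and tables by relationship to product, relationship to procedure and maximum severity. It then adds that "the following AE summaries will be provided for AEs collected at and after rescue visits", and names two: the overall summary and SOC/PT. For these, "denominators to be used for percentage calculation will be number of Rescued subjects". No severity or relationship table is planned for the period after rescue. On listings it says "All AEs will be presented in a subject listing with a flag indicating TEAE", with a second flag for events at or after rescue.

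Protocol 10.8 says "All safety analyses will be conducted on the Safety Analysis Set" and "TEAEs and serious AEs will be summarized in a similar manner by maximum severity and relationship to study drug and the surgical procedure". It makes no split at rescue. By SAP 5.1 and 5.3 the Safety Analysis Set is the Full Analysis Set (FAS), that is, the treated subjects. SAP 2 lets the SAP override the protocol's methods, but SAP 15 reports no changes.

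**The concern.** Safety is the secondary objective, and SAP 4.2.2 puts the incidence and severity of ocular and non-ocular TEAEs first among the safety evaluations. The basic figures wanted are the proportions of treated subjects in each arm with any TEAE and with a severe one. Under the split, the main table has the right denominator but an incomplete numerator. The after-rescue table has a different denominator and may count some of the same people again.

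The cut follows when data are collected, not cause, eye or onset. Non-ocular events, events in the other eye, and events first recorded at the rescue visit although they began earlier all leave the main tables. Protocol 9.4.1 records a change in intensity as a new event. An event that was mild before rescue and severe after it therefore stays mild in the maximum-severity table.

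The gap may differ between arms. Protocol 4.5 reports, without figures, that cells alone did worse than co-injection on several measures, including need for rescue. That bears on the cells-alone arm against the combination arms. The documents are silent on rescue with Y-27632 alone and across the three combination doses.

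**Working it through.** **1. What is tabulated, side by side**

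| TEAE output | Protocol 10.8 | SAP main tables (14.1, cut by 7.9) | SAP after-rescue tables (14.1) |
|---|---|---|---|
| Overall | Treated subjects, by arm | Events before rescue, over treated subjects | Events at or after rescue, over rescued subjects |
| SOC/PT | Coded; layout not specified | Events before rescue, over treated subjects | Events at or after rescue, over rescued subjects |
| Maximum severity | Treated subjects, no rescue cut | Events before rescue only | None |
| Relationship to product and to procedure | Treated subjects, no rescue cut | Events before rescue only | None |

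SAP 6.1 presents safety summaries by treatment group where appropriate, so the after-rescue tables may also be split by arm. Event counts could then be added across the two sets. Subject counts could not, because one subject can be in both.

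**2. Size of the gap for any TEAE**

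The plan states no TEAE or rescue rate for this trial, so there is no figure to reproduce. The one input from the documents is about 20 subjects per arm (SAP Table 1). All other counts are assumptions.

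Let m be the subjects with a TEAE in the main table, and a the rescued subjects with a TEAE at or after rescue. The number of distinct subjects is m + a minus the overlap, and the overlap is unknown. The rate per treated subject therefore lies between max(m, a)/20 and (m + a)/20. With m = 8 (8/20 = 40% in the main table):

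| Rescued | With a later TEAE (a) | After-rescue table | Rate per treated subject |
|---|---|---|---|
| 0 | 0 | none | 8/20 = 40% |
| 1 | 1 | 1/1 = 100% | 8/20 to 9/20 = 40% to 45% |
| 2 | 2 | 2/2 = 100% | 8/20 to 10/20 = 40% to 50% |
| 4 | 3 | 3/4 = 75% | 8/20 to 11/20 = 40% to 55% |
| 6 | 5 | 5/6 = 83% | 8/20 to 13/20 = 40% to 65% |

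**3. Severe TEAEs**

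The same bounds apply, but no after-rescue severity table exists, so only the main figure is shown. Assume 1 subject severe before rescue, tabulated as 1/20 = 5%, and s subjects severe after it.

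- s = 0: 1/20 = 5%.
- s = 1: 1/20 to 2/20 = 5% to 10%.
- s = 2: 2/20 to 3/20 = 10% to 15%.
- s = 3: 3/20 to 4/20 = 15% to 20%.

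**The case against.** **14.1 may be meant to hold everything.** Its TEAE definition has no rescue cut, and it presents the after-rescue tables as additional. SAP 9, 11.2, 13.1.2 and 13.2 each repeat the exclusion; 14.1 does not. This shows that the two sections need aligning. It does not remove the point, because 7.9 covers safety tables expressly and allows separate summary as the only exception.

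**Little is lost.** Every AE is in a flagged listing. The after-rescue overall summary, if built like the main one, counts serious, treatment-related, discontinuation and fatal TEAEs. That stands: this is a reporting gap, not a loss of data. But a listing does not replace a table for a listed safety evaluation, and neither output tabulates severity or the full relationship breakdown after rescue.

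**The split is reasonable.** Keratoplasty brings its own complications, follow-up after rescue is only about a month (Protocol 8.3), and findings of lack of efficacy are not AEs (Protocol 9.3). This supports keeping the separate tables. It does not support omitting the combined ones.

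**Stronger readings that a reader might infer.**

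- *Response at visits other than Month 6 is inflated.* If rescued eyes left the denominator, 8 responders with 4 rescues among 20 would read 8/16 = 50% instead of 8/20 = 40% (assumed counts). But SAP 5.1 names the FAS as the primary population for all efficacy endpoints, and on that denominator there is no such bias. One item in the SAP 7.10 list is not visible in the public text, so the full reach of the failure rule cannot be judged. These tables are descriptive.
- *Vision loss of 15 letters or more before surgery is hidden.* That needs the undefined term rescue visit to mean the visit where the decline was found. Protocol 8.3 separates evaluation for rescue from the procedure, and SAP 7.10 and 14.3 refer to rescue surgeries and a rescue date. The surgery visit is the more natural reading, and it keeps an earlier scheduled measurement.
- *The after-rescue denominator is an oversight, or the primary result is affected.* The denominator is stated and looks deliberate. For the primary endpoint, SAP 7.10 and 13.1.1 count rescue before Month 6 as failure.

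**Conclusion.** The point holds as a gap in the planned safety tables. As SAP 7.9 and 14.1 are written, TEAE incidence per treated subject by arm over the whole study cannot be read from any table, and maximum severity and the relationship breakdown are not tabulated after rescue. This departs from Protocol 10.8 without being declared in SAP 15. The SAP is entitled to make the change, but not to leave it unlisted.

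The size depends on rescue counts that the documents do not give. With 20 treated, 8 in the main table and 3 of 4 rescued subjects with a later TEAE, the true figure is somewhere from 40% to 55%. With 1 subject severe before rescue and 2 after, it is 10% to 15% against a tabulated 5%. With no rescues there is no effect. Late response and vision loss need clarifying only; neither is an established error. The change should be made because it improves two listed safety evaluations at little cost.

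**What to change.** 1. In SAP 14.1, add TEAE tables by arm on the Safety Analysis Set that use every TEAE, whether recorded before, at or after rescue: overall, SOC/PT, maximum severity, relationship to product and relationship to procedure. Keep the two after-rescue tables as a supplement, and amend the exception in 7.9 so that the sections agree.
2. In SAP 15, list the rescue-data rule of 7.9 as a change from Protocol 10.8.

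Two clarifications are also worth a sentence each.

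- State that by-visit response percentages at scheduled visits other than Month 6 use the FAS, with rescued eyes as non-responders. Do not apply this to the optional Month 2 visit, where attendance is discretionary. At the Month 6 report, Months 9 and 12 will not yet be due for everyone (SAP 7.1), so for those visits the rule belongs to the final report.
- In 7.9, define rescue visit by the date of rescue surgery. If the sponsor had meant the visit where the decline was found, this could change which BCVA and CCT values enter the Month 6 ANCOVA with last observation carried forward, and could change the completer analysis. The choice should be fixed before unmasking.

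The cost is SAP wording and a few table shells, with no new data and no change to the primary analysis. The small downside is that the all-TEAE tables will include some keratoplasty complications, which the retained after-rescue tables let a reader see separately.

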7.10 Missing Data Imputation for Efficacy Endpoints

The study primary endpoint is proportion of subjects having a ≥ 15 -letter improvement (3-line gain) from baseline in best-corrected visual acuity (BCVA) at Month 6. For the primary analysis, intercurrent events will be addressed using composite variable strategies. That is subjects who received any rescue surgeries prior to Month 6 or drop out the study due to any reasons prior to Month 6 will be imputed as treatment failure (i.e. not improve by ≥ 15 letters).

For the statistical analysis, the following two binary endpoints will be imputed using the same method as the primary endpoint:

- proportion of subjects having a ≥ 10 -letter improvement (2-line gain) from baseline in best-corrected visual acuity (BCVA) at Month 6
-

In addition, the following two continuous endpoints will be imputed using last observation carried forward (LOCF) for their statistical analyses:

- best-corrected visual acuity (BCVA)
- central corneal thickness (CCT)

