13.2 Secondary Efficacy Endpoints

Change from baseline in BCVA and CCT at Month 6 will be analyzed using Analysis of covariance (ANCOVA) for the full analysis set. The model will include treatment arm as a categorical variable and baseline as a covariate. Treatment comparison of BCVA and CCT at Month 6 will be conducted. Point estimates, 95% confidence intervals and p-values will be provided. Any data collected at and after rescue visits will not be used. As stated in Section 7.10, LOCF will be used to impute the missing values.

Proportion of subjects having ≥ 10 -letter improvement (2-line gain) from baseline in BCVA at Month 6 will be analyzed using the same method as the analyses of the primary endpoint. For this analysis, missing data will be imputed using the same method as the primary endpoint.

Descriptive summary statistics will be provided for all the secondary endpoints listed in Section 4.2.1.2. Any data collected at and after rescue visits will not be used.

In addition, 3, 2, and 1-line gain and 3, 2, and 1-line loss in BCVA will be summarized by dose and visit. Change from baseline within 10 letters (<10 letters gain and <10 letters loss) will be labeled as 0-line and will also be part of the summary. Summaries will include count, percentage and cumulative percentages. Any data collected at and after rescue visits will not be used.

Change from baseline in BCVA and CCT will also be summarized descriptively using LOCF imputation. Any data collected at and after rescue visits will not be used.

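### Dropping BCVA and CCT measured at the rescue visit, then applying LOCF, lets an eye that fails the primary endpoint enter the Month 6 ANCOVA with a value from before its decline

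*SAP*

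**What the plan says.** - **Rescue data.** SAP 7.9: "any data collected at and after rescue visits will not be used for the analyses and summary tables". Such values appear in listings only. The rule covers efficacy and safety tables; adverse events are the one exception.
- **Binary endpoints.** In SAP 7.10, "intercurrent events will be addressed using composite variable strategies": "subjects who received any rescue surgeries prior to Month 6 or drop out the study due to any reasons prior to Month 6" are scored as failures for 15-letter response, and 10-letter response at Month 6 follows the same rule. SAP 13.1.1 adds subjects with missing data at Month 6.
- **Continuous endpoints.** For BCVA and CCT, SAP 7.10 says that "the following two continuous endpoints will be imputed using last observation carried forward (LOCF) for their statistical analyses".
- **Secondary model.** SAP 13.2: "Change from baseline in BCVA and CCT at Month 6 will be analyzed using Analysis of covariance (ANCOVA) for the full analysis set". The same paragraph excludes rescue-visit data and adds "As stated in Section 7.10, LOCF will be used to impute the missing values".
- **Trigger for rescue.** Protocol 8.3: "Subjects whose clinical status declines in the study eye may be evaluated for rescue surgery". The section gives no earliest time.
- **Schedule.** After surgery, BCVA is first scheduled at Week 4 (Day 30 ± 7 days) and CCT at Week 1 (Day 8 + 2 days). Day 2 and Week 1 have uncorrected acuity only (Protocol 8.4.3 to 8.4.5 and Appendix 1).

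**The concern.** Rescue is considered when an eye declines, so the rescue visit is a likely place for that decline to be measured. SAP 7.9 deletes that measurement and LOCF replaces it with an earlier one. The same eye may then be a failure for response and a gain for mean change.

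This matters most if rescue differs by arm. The stated aim is to show what each component contributes, and SAP 6.2 compares every combination arm with each component. Protocol 4.5 reports that cells given alone (n = 20) did worse than co-injection on several measures, rescue among them, although it gives no rate. If the component arms have more rescues, their mean change is made to look better and the contrasts shrink. No planned analysis would show this, because the sensitivity analyses in SAP 13.1.2 cover only the primary endpoint.

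There is also a gap. An eye rescued at or before its Week 4 visit has no scheduled post-baseline BCVA that may be used, yet its Week 1 CCT could be carried to Month 6. The SAP does not say whether baseline BCVA is carried or the eye leaves the model.

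**Working it through.** **Inputs.** The documents give about 20 subjects per arm in five arms (5 × 20 = 100, as planned). They give no power, effect size, SD or rescue rate, so there is no plan figure to reproduce. Every rescue count and letter value below is an assumption.

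**One eye (invented values).** Baseline 40 letters; Week 4 58 (+18); Month 3 56 (+16); rescue visit at Month 4.5 33 (−7). Primary endpoint: failure. Month 6 ANCOVA under the SAP: +16. The gap is 16 − (−7) = 23 letters for the eye, or 23/20 = 1.15 letters on the arm mean.

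**Shift in one arm's unadjusted mean.** With r rescued eyes, carried change G and discarded rescue-visit change V, the shift is r × (G − V)/20.

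| r | G = +5, V = 0 | G = +10, V = −10 | G = +15, V = −10 |
|---|---|---|---|
| 1 | 0.25 | 1.0 | 1.25 |
| 2 | 0.5 | 2.0 | 2.5 |
| 4 | 1.0 | 4.0 | 5.0 |
| 6 | 1.5 | 6.0 | 7.5 |
| 8 | 2.0 | 8.0 | 10.0 |

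For CCT the same expression applies in microns with the sign turned round, since a fall is the improvement.

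**Shift in a contrast.** If G − V is the same in both arms, the combination-minus-component difference is understated by (r_component − r_combination) × (G − V)/20. All three cases below take 1 rescue against 6.

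*Case A: non-rescued means +15 and +8, G = +10, V = −10.*
- SAP rule: (19×15 + 10)/20 − (14×8 + 60)/20 = 14.75 − 8.60 = 6.15
- Rescue-visit value: (285 − 10)/20 − (112 − 60)/20 = 13.75 − 2.60 = 11.15
- Change 0: 285/20 − 112/20 = 14.25 − 5.60 = 8.65

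A simulated two-arm ANCOVA (3,000 runs, residual SD 12) gave 6.1, 11.1 and 8.6. The 5.0-letter gap between the first two compares with a standard error of 12 × √(2/20) = 3.8.

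*Case B: non-rescued means +18 and +5, G = +6, V = −4.*
- SAP rule: 17.4 − 5.3 = 12.1
- Rescue-visit value: 16.9 − 2.3 = 14.6
- Change 0: 17.1 − 3.5 = 13.6

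*Case C: as B, but the rescued eyes never gained (G = −5, V = −15).*
- SAP rule: 16.85 − 2.00 = 14.85
- Rescue-visit value: 16.35 − (−1.00) = 17.35
- Change 0: 13.6

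In B and C the SAP rule falls 5 × 10/20 = 2.5 letters short of the rescue-visit value. Against change 0 it is lower in B and higher in C, so that comparison depends on the sign of G.

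**Balanced rescue.** With 3 against 3 (other inputs as in Case A) the simulated difference was 6.0 under both the SAP rule and the rescue-visit value. Both arm means are still raised, by 3 × 20/20 = 3 letters.

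**Early rescue.** If eyes without a post-baseline BCVA left the model, 1, 2, 4 or 6 such rescues would leave 19, 18, 16 or 14 of 20. If baseline were carried, all 20 would stay with change 0. The SAP does not choose between these.

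**The case against.** The strongest reply is that the SAP never defines the rescue visit. SAP 14.3 works with surgeries and a rescue date, and Protocol 8.3 requires evaluation and consultation before any procedure. A decline may therefore be recorded at an earlier visit, in which case LOCF carries the lower value. SAP 14.3 also counts surgeries given when the criteria were not met, so not every rescue follows a decline. This stands: the outcome is possible for an eye, not certain.

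A reader might infer that early-rescued eyes drop out of the ANCOVA. The documents do not say so. SAP 7.10 imputes the BCVA value without limiting LOCF to post-baseline data, and the model is on the full analysis set, so carrying baseline is a permitted reading. An unscheduled BCVA is also possible (Protocol 8.4.12), although SAP 6.5 mentions unscheduled visits only for baseline and listings. What remains is a missing rule.

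A reader might also infer that the rule flatters the component arms by a known amount. No rescue rate is given for any arm, and rescued eyes in an arm without cells may never have gained. Case C shows that the direction against change-0 scoring can then reverse. It does not rescue the rule, because discarding a value worse than the carried one still raises the arm mean.

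Finally, the study is unpowered, its p-values are nominal, and rescue stays visible through counts, Kaplan-Meier plots and listings. Treating a binary and a continuous endpoint differently is not in itself an error. All of that limits the harm. But SAP 7.3 gives estimates for future designs as the purpose, and biased estimates damage exactly that.

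**Conclusion.** The concern holds as a flaw in the scoring rule. SAP 7.9, 7.10 and 13.2 together discard BCVA and CCT from the rescue visit and carry an earlier value, so a primary-endpoint failure can contribute a pre-decline value to the Month 6 ANCOVA. On the assumed inputs the arm mean is too favourable by 0.25 to 10 letters, and a contrast with 1 against 6 rescues is understated by 2.5 to 5 letters. These figures show direction and scale only. The effect on contrasts is small if rescues are few or balanced, and nil for any eye whose decline is already in the carried value. If rescue is commoner in the component arms, the bias runs against the combination, so the documents give no ground for saying that the rule would manufacture a benefit. The treatment of eyes with no post-baseline BCVA is unspecified and should be settled before unmasking.

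**What to change.** These are changes to the analysis only.

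1. In SAP 7.9, 7.10 and 13.2, exclude only BCVA and CCT measured after the rescue surgery. The last measurement before surgery, scheduled or unscheduled and where available, is then the one carried. The surgery date becomes the cut-off, so the undefined term no longer matters for these endpoints.
2. State that baseline is carried (change 0) when no post-baseline value exists, so that every subject in the full analysis set is in the model.
3. Add one supportive Month 6 ANCOVA each for BCVA and CCT with change set to 0 for all subjects whom the primary endpoint imputes as failures: rescue, dropout or missing at Month 6. Limiting it to rescued eyes would not match the primary rule.

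The cost is SAP wording and one extra model run per endpoint. Two limits remain. Protocol 8.3 asks for examination findings only as available, so some eyes may have no measurement just before surgery. Change 0 is an assigned value and may itself be optimistic for an eye that worsened.
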